8.5.2 Follow-up of Serious Adverse Events

All SAEs should be followed up until resolution or stabilization. The timelines and procedure for follow-up reports are the same as those for the initial report.

New information regarding an SAE that becomes available after the submission of the initial SAE Notification Form must be reported by the Investigator to the Sponsor by completion of a SAE Follow-up Report Form or through other written documentation (e.g., laboratory tests, discharge summary, postmortem results). Follow-up reports and/or written documentation must be provided to the Sponsor within 24 hours of the Investigator's receipt of the information.

8.5.3 Reporting of Death

Death is an outcome of an SAE and not an SAE itself. When death is an outcome, the event(s) resulting in death should be reported (e.g., “pulmonary embolism” with a fatal outcome).

8.6 Post-Trial Adverse Events

Any AE that occurs outside of the protocol-specified observation period or after the end of the study but is considered to be caused by the investigational product must be reported to the Sponsor. Instructions for how to submit these AEs will be provided separately.

8.7 Pregnancy Reporting and Follow-up

Pregnancy in a female clinical trial subject is not an SAE, however, complications of such pregnancies, for example, spontaneous abortion, may qualify as an SAE and should be reported as an SAE even if they occur after the SAE reporting period has ended.

The Investigator must notify the Sponsor via telephone or e-mail within 24 hours of awareness of a pregnancy in a study subject and must complete the Pregnancy Notification Form and submit it to the Sponsor within 2 working days of being notified. If the female subject is pregnant, then subject will not receive any further doses of their assigned study drug. The pregnancy must be followed to determine outcome, including spontaneous or voluntary termination, details of birth, and the presence or absence of any birth defects, congenital abnormalities, or maternal and/or newborn complications. This follow-up should occur even if the intended duration of safety follow-up for the trial has ended. Information regarding the course of the pregnancy, including perinatal and postnatal offspring outcome up to 8 weeks of age should be reported as follow-up information on the Pregnancy Notification Form.

Male study subjects will be instructed to notify the Investigator if a female partner becomes pregnant during the study. The Investigator must notify the Sponsor within 24 hours via telephone or e-mail and must complete the Pregnancy Notification Form and submit it to the Sponsor within 2 working days of being notified. The Investigator should obtain informed consent from the subject's partner using an EC-approved ICF, allowing the Investigator to obtain information regarding the pregnancy and its outcome. If the subject's partner provides informed consent, the Investigator should follow the pregnancy until outcome as described above for female study subjects and report the follow-up information on the Pregnancy Notification Form.

8.8 Stopping Rules

Safety data will be reviewed on an ongoing basis by the Sponsor's Medical Officer and the CRO Medical Monitor (Section 3) who will monitor subject safety during study conduct and can make decisions regarding individual subject drug, group/cohort treatment, and/or subsequent dosing regimens. The grading of events can be used to help determine these decisions, taking into consideration the subject's baseline parameters and the possibility for differences based on demographics.

Potential safety signals that will trigger a meeting of the Sponsor and CRO medical personnel, and subsequent written recommendation about study conduct include the following:

- Any SAE considered to be related to study drug
- Any related clinical NCI CTCAE \geq grade 3 (severe) AE
- Any unrelated similar SAE or clinical NCI CTCAE \geq grade 3 (severe) AE in ≥ 2 subjects. For example, wheezing and chest tightness would be considered similar because they may both be related to airway obstruction.

As noted in Section 6.14.1 study drug will be discontinued in subjects with a decrease from Baseline in FEV1 of $\geq 15\%$ associated with a decrease from Baseline in the FEV1/FVC ratio.

Related AEs or suspected adverse drug reactions means that a causal relationship between a medicinal product and an AE is at least a reasonable possibility, i.e., there is evidence to suggest a causal relationship.

When a potential safety signal as defined above occurs, enrollment will be halted pending review by the Sponsor Medical Officer and CRO Medical Monitor and study treatment will be stopped in the individual experiencing the safety signal AE. All potential safety signals will be reviewed within 7 days by the Sponsor Medical Officer and CRO Medical Monitor that could recommend:

- Re-start subject enrollment. A protocol amendment summarizing available data and justification will be required to continue enrollment at the dose level associated with a stopping rule or any higher dose.

- Add a new lower dose cohort
- Add more subjects to a cohort without dose limiting toxicities
- Continued pausing of enrollment
- Permanently discontinuing enrollment into the study

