8.3 Adverse Event Classification

8.3.1 Relationship to Investigational Product

The Investigator's assessment of causality must be provided for all AEs (serious and non-serious). An Investigator's causality assessment is the determination of whether there exists a reasonable possibility that the investigational product caused or contributed to an AE.

- Not related: The AE is clearly not related to the study drug, or the temporal relationship of the onset of the AE relative to administration of the product is not reasonable, or the AE can be explained by another cause such as an underlying medical condition or other concomitant medication, or the AE has no plausible relationship to study drug.
- Related: The AE is probably related to the study drug. The temporal relationship of the AE to administration of the product is reasonable and there is no other cause to explain the event. Adverse events should be classified as related if the Investigator feels there is evidence to suggest a causal relationship between the study drug and the AE.

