8.3.2 Severity

All adverse Events will be assessed according to the National Cancer Institute (NCI) Common Terminology Criteria for Adverse Events (CTCAE), Version 5.

Table 4 will be used for assessing severity for AEs that are not specifically listed in the NCI CTCAE.

Table 4 Adverse Event Severity Grading Scale for Events not Specifically Listed in NCI CTCAE

Grade	Severity
1	Mild; asymptomatic or mild symptoms; clinical or diagnostic observations only; or intervention not indicated
2	Moderate; minimal, local, or non-invasive intervention indicated; or limiting age-appropriate instrumental activities of daily living [a]
3	Severe or medically significant, but not immediately life-threatening; hospitalization or prolongation of hospitalization indicated; disabling; or limiting self-care activities of daily living [b, c]
4	Life-threatening consequences or urgent intervention indicated [d]
5	Death related to adverse event [d]

a. Instrumental activities of daily living refer to preparing meals, shopping for groceries or clothes, using the telephone, managing money, etc.

b. Examples of self-care activities of daily living include bathing, dressing and undressing, feeding oneself, using the toilet, and taking medications, as performed by patients who are not bedridden.

c. If an event is assessed as a "significant medical event," it must be reported as a serious adverse event, per the definition of serious adverse event in Section 8.2.2.

d. Grade 4 and 5 events must be reported as serious adverse events, per the definition of serious adverse event in Section 8.2.2.

Reference source: Common Terminology Criteria for Adverse Events (CTCAE) version 5.0 published on November 27, 2017.

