8.5 Collection and Reporting of Serious Adverse Events

8.5.1 Initial Serious Adverse Event Reports

All SAEs that occur up to and including EOS must be reported by the Investigator to the Sponsor within 24 hours of awareness of the event by submission of a SAE Notification Form. Investigators must report to the Sponsor any SAE, whether or not considered drug related, including those listed in the protocol or IB.

The initial report must contain at a minimum the protocol number, a subject study identifier code, subject's initials, subject's date of birth, an event term, the suspected product and an assessment of causality. An Investigator may be requested by the Sponsor to obtain specific follow-up information in an expedited fashion. This information may be more detailed than that captured on the AE CRF. In general, this will include a description of the SAE in sufficient detail to allow for a complete medical assessment of the case and independent determination of possible causality.

Information on other possible causes of the event, such as concomitant medications and illnesses must be provided. In the case of a subject death, a summary of available autopsy findings must be submitted as soon as possible to the Sponsor.

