### 8.1.2. Relationship of Adverse Events to Study Drug

The Investigator's assessment of causality must be provided for all AEs (serious and non-serious). An Investigator's causality assessment is the determination of whether there exists a reasonable possibility that the investigational product caused or contributed to an AE.

- Not related: The AE is clearly not related to the study drug, or the temporal relationship of the onset of the AE relative to administration of the product is not reasonable, or the AE can

be explained by another cause such as an underlying medical condition or other concomitant medication, or the AE has no plausible relationship to study drug.

- Related: The AE is probably related to the study drug. The temporal relationship of the AE to administration of the product is reasonable and there is no other cause to explain the event. Adverse events should be classified as related if the Investigator feels there is evidence to suggest a causal relationship between the study drug and the AE.

Study drug related TEAEs will be summarized by SOC and PT for each treatment (active treatments, active treatment total, and pooled placebo) and overall.

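### The middle wording of Protocol 8.3.1 and SAP 8.1.2 defines a related AE more strictly than stopping rule 8.8 does, and the mandatory FEV1 discontinuation rule uses a spirometry Baseline that only the SAP defines

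*Protocol*

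**What the plan says.** **Causality.** Protocol 8.3.1 requires the investigator's causality judgement for every AE and frames the question as whether a drug contribution is reasonably possible. It then gives two categories. Not related includes the case where "the AE can be explained by another cause such as an underlying medical condition or other concomitant medication". Related starts higher, in words that SAP 8.1.2 repeats: "The AE is probably related to the study drug". It continues: "The temporal relationship of the AE to administration of the product is reasonable and there is no other cause to explain the event". It ends more loosely, saying that AEs "should be classified as related if the Investigator feels there is evidence to suggest a causal relationship".

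Protocol 8.8 carries its own definition: related means that "a causal relationship between a medicinal product and an AE is at least a reasonable possibility". One related SAE, or one related clinical AE of Grade 3 or above, is a signal that halts enrollment. Unrelated events count once similar ones occur in at least two subjects. Section 8.8 does not say whose judgement of related sets off the trigger. A halt has consequences: "A protocol amendment summarizing available data and justification will be required to continue enrollment at the dose level associated with a stopping rule", or at any higher dose.

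**FEV1.** Protocol 6.14.1 and 8.8 make discontinuation of study drug mandatory when FEV1 falls 15% from Baseline together with a fall in the FEV1/FVC ratio. Protocol 6.7 schedules spirometry at Screening and before dosing on Day 1, but names neither as Baseline. SAP 4.1 and 8.6 define it as the mean of the Day 1 pre-dose value and the screening value from the same equipment. SAP 8.6 adds that screening spirometry should be repeated on the clinic device if the first test used another one. That repeat test is not in Protocol 6.7 or 7.1.

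**The concern.** Both rules protect subjects from the toxicity that limited dosing in Phase 1a. At 40 mg once daily, three healthy volunteers had TEAEs secondary to airflow limitation that appeared reversible (Protocol 1.1.1.3). The lower doses were well tolerated.

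Every subject here has a lung disease that can be offered as another cause of a respiratory event. That is where the strict middle wording of 8.3.1 and the looser test in 8.8 part company. The label decides whether one event or two similar ones meet the listed trigger. It also decides what enters the related-TEAE summary in SAP 8.1.2.

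The FEV1 rule has to be applied at the visit, from readings 30 and 60 minutes after dosing. Site staff work from the protocol, so the definition they need sits in a document they would not normally consult.

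**Working it through.** **1. The plan's own figure.** Protocol 9.5 gives a 60% and an 85% chance of seeing an AE among 18 treated subjects at true rates of 5% and 10%. 1 − 0.95^18 = 60.3% and 1 − 0.90^18 = 85.0%. Both reproduce, and neither is in dispute.

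**2. The causality tests side by side.**

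| Place | Test in substance | Against 8.8 |
|---|---|---|
| 8.3.1, opening | drug contribution reasonably possible | same |
| 8.3.1, Not related | another cause can explain the event | stricter |
| 8.3.1, Related, first two sentences | probable, with no other cause | stricter |
| 8.3.1, Related, last sentence | evidence suggests causation | same |
| 8.8 | at least reasonably possible | reference |

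Take a non-serious Grade 3 respiratory event that IPF could explain but to which the drug may reasonably have contributed. The middle of 8.3.1 makes it not related; 8.8 makes it related. Exposure is mainly at this level. The note to Table 4 in 8.3.2 says "Grade 4 and 5 events must be reported as serious adverse events", and 8.5.1 requires SAE reports detailed enough for "independent determination of possible causality".

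**3. What the label could do to the halt trigger (illustration only).** The documents give no Grade ≥3 rate at these doses and no misclassification share, so both are assumed. Let n = 9 active subjects in a cohort, p = the rate of Grade ≥3 events per subject, all related under 8.8, and f = the share marked not related on the form. Only the listed triggers are counted.

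- 8.8 definition applied: 1 − (1 − p)^9
- Form label controls, all events similar: 1 − (1 − p)^9 − f·9p(1 − p)^8
- Form label controls, no two events similar: 1 − (1 − p(1 − f))^9

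| p | 8.8 applied | Form label, similar, f = 25 / 50 / 100% | Form label, none similar, f = 25 / 50 / 100% |
|---|---|---|---|
| 1% | 8.6% | 6.6 / 4.5 / 0.3% | 6.6 / 4.4 / 0% |
| 2% | 16.6% | 12.8 / 9.0 / 1.3% | 12.7 / 8.6 / 0% |
| 5% | 37.0% | 29.5 / 22.0 / 7.1% | 29.1 / 20.4 / 0% |

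If 8.8's definition is used for the trigger, the first column applies and the gap is zero. The f = 100% entries are a limit, since they need every investigator to ignore the last sentence of 8.3.1 every time.

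**4. One subject near the FEV1 threshold (assumed values).** Let FEV1 be 2.50 L at screening, 2.30 L before dosing on Day 1 and 2.00 L after dosing.

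| Baseline used | Value | 85% of it | Fall to 2.00 L |
|---|---|---|---|
| Screening | 2.50 L | 2.125 L | 20.0% |
| Day 1 pre-dose | 2.30 L | 1.955 L | 13.0% |
| SAP mean | 2.40 L | 2.040 L | 16.7% |

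If the ratio has also fallen, the subject stops under two readings and continues under the third.

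**5. Effect over many subjects.** This was simulated with 2,000,000 subjects per setting. Screening, Day 1 and post-dose values have independent normal error, with FEV1 CV 3% or 5% and ratio SD 0.01 or 0.02 around 0.80. True FEV1 falls of 10, 15 and 20% are paired with ratio falls of 0.04, 0.06 and 0.08. The rule is met if post-dose FEV1 is at most 0.85 × Baseline and the ratio is below its Baseline. The overall chance of meeting the rule differs by 0–4 percentage points between definitions. The SAP mean is slightly more accurate: it stops fewer subjects at a true 10% fall and more at a true 20% fall, because it averages two readings.

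**The case against.** On causality, the operative tests already agree. The last sentence of 8.3.1 and the gloss in 8.8 both turn on evidence suggesting causation, and it is natural to read a stopping rule by its own definition. The investigator is the obvious default assessor, because 8.3.1 demands that judgement for every AE and the synopsis records an investigator-attributed relationship. This stands as far as it goes: it makes the halt gap zero for anyone who reads 8.8 that way. It does not cure the form, which is completed under 8.3.1, or the related-TEAE table built from it.

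A reader might infer that an event marked not related cannot halt the trial until a second similar one occurs. The documents do not support that. The signals in 8.8 are introduced as included examples, and the medical officer and medical monitor may act on ongoing review. These powers are discretionary, so they reduce the risk without saying which definition controls the mandatory trigger.

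The alternative-cause limb also has a legitimate use. Bronchoscopy follows the Day 14 dose by about 2–3 hours and can cause events of its own. Deleting the limb outright would remove a proper ground for calling those events unrelated.

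On FEV1, other grounds in 6.14.1 (an unacceptable AE, investigator or sponsor discretion) provide a backstop, and the general rule in SAP 4.1 arguably supplies a Day 1 fallback. Both points stand, but neither tells a site which value the 15% is measured from. A reader who simulates paired decisions might infer that the choice between Day 1 and Screening changes a large share of them. That would be a misreading: two repeat Day 1 tests disagree as often, so it is test-retest noise.

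**Conclusion.** Both parts hold, within limits.

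(a) Protocol 8.3.1 and SAP 8.1.2 are internally inconsistent, and their middle wording is stricter than 8.8. The exposure is mainly non-serious Grade 3 events with a plausible other cause, plus a possible undercount of related TEAEs. The size cannot be determined from the documents. The halt percentages above rest on assumed rates and shares, and the gap is zero if 8.8's definition is applied.

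(b) The mandatory FEV1 rule depends on a Baseline that the protocol leaves undefined for spirometry. This is a gap and not a conflict between the documents. The overall effect is modest, 0–4 percentage points under the assumed CVs and ratio SDs, but two sites could treat the same borderline subject differently.

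It should not be inferred that the primary endpoint is compromised. Incidence of any TEAE depends neither on the causality label nor on the spirometry Baseline. The changes are worth making because these are safety rules and the new wording is short.

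**What to change.** **Causality.** In Protocol 8.3.1 and SAP 8.1.2, define related as at least a reasonable possibility of a drug contribution. Delete the word *probably* and the requirement that no other cause exist. Keep the alternative-cause limb only where the other cause, such as the bronchoscopy, leaves no reasonable possibility that the drug contributed. State in 8.8 that its definition governs the triggers, and that an assessment of related by either the investigator or the medical officer or medical monitor suffices.

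**FEV1.** Copy the SAP 4.1/8.6 Baseline and the same-device screening test into Protocol 6.7, 7.1, 6.14.1 and 8.8. Name the Day 1 pre-dose value as the fallback when no same-device screening value exists.

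**Cost.** A substantial amendment with IRB/IEC approval (Protocol 10.4, 12.2), a SAP update, site retraining, and one extra screening spirometry where the first test used other equipment. A few more events may be called related, and enrollment may pause more often. There are no extra pauses from the wording if 8.8 is already applied to the triggers. If the form label controls now, an upper bound per 12-subject cohort compares at least one event, 1 − (1 − p)^12, with at least two similar ones, 1 − (1 − p)^12 − 12p(1 − p)^11. It treats every background Grade ≥3 event as newly related. At assumed rates of 1, 2 and 5% it gives 11.4% against 0.6%, 21.5% against 2.3%, and 46.0% against 11.8%. Keeping the limited alternative-cause limb should hold the true figure below that bound. Each pause is reviewed within 7 days, but continuing at that dose or higher needs an amendment, so the cost is real.

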8.9 Emergency Unblinding

The blind may be broken for an individual subject at the discretion of the Investigator if knowledge of the type of study drug administered is required to guide appropriate treatment decisions. The Sponsor's Medical Officer should be notified within 24 hours of the Investigator's decision to unblind.

8.10 Emergency Sponsor Contact

In a medical emergency (i.e., an event that requires immediate attention regarding operation of the clinical study and/or the use of investigational study drug), study site staff will apply appropriate medical intervention according to current standards of care and contact the Sponsor's Medical Officer.

9 STATISTICAL CONSIDERATIONS

9.1 Statistical and Analytical Plans

A statistical analysis plan (SAP) will be created, which will provide a more technical and detailed description of the proposed data analysis methods and procedures.

The results of the final analysis, as well as any deviations from planned statistical analyses, will be presented in the clinical study report.

9.1.1 Randomization Procedures

Subjects will be randomized to receive LTI-03: placebo in sequential cohorts, as per the study design. Randomization codes and unique subject identification numbers will be generated by the IVRS. All study staff will remain blinded to study drug assignment.

9.2 Study Hypotheses

The primary endpoint of the study is safety. No formal statistical hypotheses will be tested.

9.3 Analysis Set

The populations for analysis will include at a minimum a Safety Analysis Set. Other potential analysis sets will be defined in the SAP.

9.3.1 Safety Analysis Set

The Safety Analysis Set will consist of all subjects randomized to study drug and received at least 1 dose of study drug.

9.4 Statistical Methods and Analysis

9.4.1 General Approach

All descriptive statistical analyses will be performed using the most recently released and available Statistical Analysis System (SAS) statistical software (version 9.4 or higher), unless otherwise noted. For categorical variables, the number and percent of each category within a parameter will be presented. For continuous variables, the sample size (n), mean, median, and standard deviation, as well as the minimum and maximum values, will be presented. Missing data will not be imputed unless otherwise stated. Subjects on Placebo from all cohorts will be pooled to form a combined placebo group for analysis.

9.4.2 Demographics and Other Baseline Characteristics

Demographics and other baseline disease characteristics will be summarized by treatment and\or cohort.

9.4.3 Concomitant Medications

Concomitant medications will be coded using the latest version of the World Health Organization Drug Dictionary (WHO-DD).

